7.5.4.6 Adverse Event Assessment of Clinical Laboratory and Other Safety Parameters

For any abnormal laboratory test results (hematology, blood chemistry, or urinalysis) or other safety assessments (eg, physical examination, vital signs) that occur or worsen following exposure to cefiderocol from baseline, the investigator or subinvestigator will consider whether those results are clinically significant. Abnormal laboratory test results are defined as values outside the RR. For test results which are abnormal at baseline and significantly worsen following the initiation of the study, the investigator or subinvestigator must also consider whether those results are clinically significant. Any test results which are considered to be clinically significant by the investigator or subinvestigator are to be recorded as AEs. If abnormal laboratory finding is associated with disease or organ toxicity, the investigator should report only the disease or organ toxicity as an AE. These AEs should also be assessed as to whether or not they meet the definition of serious and should be reported accordingly.

The investigator or subinvestigator will consider test results to be clinically significant in the following circumstances (at their own discretion in the other circumstances):

- Clinical laboratory test results that lead to any of the outcomes included in the definition of an SAE ([Section 7.5.4.7.1](#)).
- Clinical laboratory test results that lead to a change in dosing of study treatment or discontinuation from the study.
- Clinical laboratory test results that lead to a concomitant drug treatment or other therapy.
- Clinical laboratory test results that require additional diagnostic testing (except for a confirmatory test) or other medical intervention.
- Clinical laboratory test results that meet the management and discontinuation criteria for abnormal liver function tests or transaminase elevations identified in [Appendix 2](#).

In addition, when any test result meets the management and discontinuation criteria for liver function abnormalities or transaminase elevations ([Appendix 2](#)), the results of further assessments and required follow-up should be recorded in the Liver Event Form in the eCRF.

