9.11.3 Clinical Laboratory Analysis

Summary statistics for select laboratory parameters will be presented for each scheduled time point measured and for the change from baseline to each time point. Baseline will be the last value obtained prior to study treatment administration within each respective phase of the study.

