6.5. Visit Windows

Visits specified in the electronic case report form (eCRF) will be used for this study. Measurements will be performed according to the Time and Events Schedule in protocol Appendix 1. The acceptable time deviations relative to the time points specified in protocol Appendix 1 are shown in Table 6-1. Every effort will be made to adhere as closely as possible to the procedure time points specified.

Table 6-1 Acceptable Time Windows

Study Activity	Time Points		Acceptable Time Window
Screening	Can be Treatment Day 1		Within 4 days prior to Treatment Day 1
Enrollment	Treatment Day 1		---
Drug infusion	See Appendix 1		± 15 minutes
Dosing interval	See Appendix 1		± 15 minutes
Pharmacokinetic blood sampling	Cohorts 1 and 2	1 hour after start of infusion	± 15 minutes
		3 hours after start of infusion	Within 15 minutes prior to the end of infusion using a separate line or immediately after the end of infusion using the same line and with proper flushing
		3.5 hours after start of infusion	± 15 minutes
		5 and 8 hours after start of infusion	± 30 minutes
	Cohorts 3 and 4	3 hours after start of infusion	Within 15 minutes prior to end of infusion using a separate line or immediately after the end of infusion using the same line and with proper flushing
		5 and 8 hours after start of infusion	± 30 minutes
EOT	Within 24 hours after last day of study treatment		As soon as possible after last dose (same calendar day)
Posttreatment	7 days after EOT		± 4 days
EOS	28 days after last dose of study treatment		+ 7 days

EOS = End of Study; EOT = End of Treatment

EOS = End of Study; EOT = End of Treatment.

This document is confidential.

All the data, including unscheduled visits, will be included in the listings. If multiple records exist at the same visit/time point, the closest record to target day will be used for the purpose of summary tables. If these are some records that have the same difference from the target day, the latest record will be used.

This document is confidential.

7. Demographic, Other Baseline Characteristics, and Medication

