Laboratory test results will be assigned a Low/Normal/High (LNH) classification according to whether the value is below (L: low), within (N: normal), or above (H: high) the laboratory parameter's normal range; categorical laboratory test results will be classified as normal (N) or abnormal (A).

Summary statistics for laboratory test data (hematology, blood chemistry, and other specialized tests) will be presented for each scheduled time point measured after the first infusion and for the change from baseline to each time point. All clinical laboratory summaries other than specialized tests will be based on the local laboratory measurements, and only the data that can be converted into standard units will be included in analysis. The number and percentage of subjects with the following prespecified outlier category listed in Table 11-2 below at each postbaseline visit, including unscheduled visits, will be presented by cohort.

Table 11-2 The Outlier for Each Parameter in Laboratory Test

Parameter (Unit)	Outlier Category
Hemoglobin (g/dL)	Decrease from baseline ≥ 1.5 g/dL
Platelet count ($10^3/\mu\text{L}$)	Decrease from baseline $\geq 25\%$ and value $< \text{LLN}$ Increase from baseline $\geq 100\%$ and value $> \text{ULN}$
White blood cell count ($10^3/\mu\text{L}$)	Decrease from baseline $\geq 50\%$ and value $< \text{LLN}$ Increase from baseline $\geq 20\%$ and value $> \text{ULN}$
ALT (U/L)	Value $> 3 \times \text{ULN}$ Value $> 5 \times \text{ULN}$ Value $> 10 \times \text{ULN}$ Value $> 20 \times \text{ULN}$
AST (U/L)	Value $> 3 \times \text{ULN}$ Value $> 5 \times \text{ULN}$ Value $> 10 \times \text{ULN}$ Value $> 20 \times \text{ULN}$
AST (U/L) or ALT (U/L)	Value $> 3 \times \text{ULN}$ Value $> 5 \times \text{ULN}$ Value $> 10 \times \text{ULN}$ Value $> 20 \times \text{ULN}$
Total bilirubin (mg/dL)	Value $> 2 \times \text{ULN}$ Increase from baseline $\geq 50\%$ and value $> \text{ULN}$
Blood urea nitrogen (mg/dL)	Increase from baseline $\geq 50\%$ and value $> \text{ULN}$
Serum creatinine (mg/dL)	Increase from baseline ≥ 0.3 mg/dL
ALP (U/L)	Increase from baseline $\geq 50\%$ and value $> \text{ULN}$
AST (U/L) or ALT (U/L) + total bilirubin (mg/dL)	(AST $> 3 \times \text{ULN}$ or ALT $> 3 \times \text{ULN}$) and (total bilirubin $> 2 \times \text{ULN}$)

ALP = alkaline phosphatase; ALT = alanine transaminase; AST = aspartate transaminase; LLN = lower limit of normal; UN = upper limit of normal

This document is confidential.

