Baseline will be the last value obtained prior to study drug administration within each respective phase of the study.

The eGFR and microbiology data (urine and blood collection of microbiological cultures) will be listed.

The urine pregnancy test will be performed for sexually active females of childbearing potential only. The pregnancy test results will be listed.

All serum chemistry, hematology, and urinalysis results in international standard units will be presented in data listings, with any abnormal findings appropriately flagged.

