- Tabular displays of data for medical history, prior/concomitant medications, and adverse events will be presented by body system, treatment class, or System Organ Class with the highest occurrence in the active treatment group in decreasing order, assuming all terms are coded. Within the body system, drug class and System Organ Class, medical history (by PT), drugs, and adverse events (by PT) will be displayed in decreasing order. If the incidence for more than 1 term is identical, they will then be sorted alphabetically. Missing descriptive statistics or p-values that cannot be estimated will be reported as “-”.
- The percentage of subjects will normally be calculated as a proportion of the number of subjects assessed in the relevant treatment group (or overall) for the analysis set presented. However, the denominator will be selected after careful consideration of the appropriate number of subjects exposed. The details of this will be described in footnotes or programming notes.
- For categorical summaries (number and percentage of subjects) where a subject can be included in more than 1 category, a footnote or programming note will describe if the subject is included in the summary statistics for all relevant categories or just 1 category and the criteria for selecting the criteria.
- Where a category with a subheading (such as System Organ Class) has to be split over more than 1 page, the subheading will be followed by “(cont)” at the top of each subsequent page. The overall summary statistics for the subheading will only be output on the first relevant page.

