Table 14.2.1.5 Summary of Microbiological Outcome Per Baseline Gram-negative Pathogen By Time Point (MITT Population)
Table 14.2.1.6 Summary of Microbiological Outcome at Post Treatment per Baseline Pathogen and Minimum Inhibitory Concentration Values Determined by Clinical and Laboratory Standards Institute (MITT Population)
Table 14.2.2 Plasma Cefiderocol Concentration (PKCS Population)
Table 14.3.1.1 Treatment-Emergent Adverse Events – Overall Summary (Safety Population)

This document is confidential.

Table 14.3.1.2 Treatment-Emergent Adverse Events by System Organ Class and Preferred Term (Safety Population)

Table 14.3.1.3 Treatment-Emergent Adverse Events by System Organ Class, Preferred Term and Maximum Severity (Safety Population)

Table 14.3.1.4 Treatment-related Treatment-Emergent Adverse Events by System Organ Class and Preferred Term (Safety Population)

Table 14.3.1.5 Serious Treatment-Emergent Adverse Events by System Organ Class and Preferred Term (Safety Population)

Table 14.3.4.1.1 Hematology: Summary by Visit and Change From Baseline (Safety Population)

Table 14.3.4.1.2 Blood Chemistry: Summary by Visit and Change from Baseline (Safety Population)

Table 14.3.4.1.3 Urinalysis: Summary by Visit (Safety Population)

Table 14.3.4.1.4 Summary of Laboratory Tests Outside Prespecified Outlier by Visit (Safety Population)

Table 14.3.4.2 Summary of Vital Signs by Visit and Change from Baseline (Safety Population)

Table 14.3.4.3 Summary of Physical Examination by Visit (Safety Population)

This document is confidential.

16. Index of Figures

Figure 14.2.3 Mean and SD Plasma Cefiderocol Concentration Over Time by Cohort, Phase, and Infusion Time (PKCS Population)

Figure 14.3.4.1.5 Mean (Standard Deviation) Plot of Laboratory Parameters by Time Point - Hematology (Safety Population)

Figure 14.3.4.1.6 Mean (Standard Deviation) Plot of Laboratory Parameters by Time Point - Chemistry (Safety Population)

This document is confidential.

17. Index of Listings

Listing 16.2.1.1 Subject Disposition (All Subjects)
Listing 16.2.1.2 Subject Population (All Subjects)
Listing 16.2.1.3 Missing Visits Due to COVID-19 (All Enrolled Subjects)
Listing 16.2.1.4 Missing Assessments Due to COVID-19 (All Enrolled Subjects)
Listing 16.2.2.1 Major Protocol Deviations (All Enrolled Subjects)
Listing 16.2.3.1 Subject Inclusion and Exclusion Criteria Deviations (All Screened Subjects)

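### SAP 11.3 counts Table 11-2 laboratory outliers visit by visit; a count of children who ever met each category after baseline should be added

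*SAP*

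**What the plan says.** SAP 11.3 defines a set of laboratory outlier categories in Table 11-2. It states that the number and percentage of subjects with the "prespecified outlier category listed in Table 11-2 below at each postbaseline visit, including unscheduled visits, will be presented by cohort". The Index of Tables (SAP 15) has one matching output: "Table 14.3.4.1.4 Summary of Laboratory Tests Outside Prespecified Outlier by Visit (Safety Population").

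Other text that bears on the point:

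- **Protocol 9.11.3** is narrower: "Summary statistics for select laboratory parameters will be presented for each scheduled time point measured", together with change from baseline.
- **SAP 6.5** deals with several records at one visit or time point: "the closest record to target day will be used for the purpose of summary tables".
- **SAP 6.1** puts repeat and unscheduled assessments in the listings. SAP 11.3 says the laboratory results "will be presented in data listings, with any abnormal findings appropriately flagged".
- **Protocol 2** lists clinical laboratory assessments among the primary endpoints.
- **SAP 11.2.1** does plan a once-per-child summary for adverse events: subjects with at least one treatment-emergent event, and events by maximum severity.

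**The concern.** Safety after multiple dosing is a primary objective, and the cohorts are small. For each laboratory threshold, the first thing a reader wants to know is how many of these children ever crossed it. A table of separate visit counts does not answer that. The same child may be abnormal at three visits, or three different children at one visit each, and both cases produce the same row of counts.

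The SAP already reports adverse events per child, so laboratory outliers are treated less fully than events although both are primary endpoints. As specified, the per-child count would have to be assembled by hand from the listings.

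**Working it through.** **Inputs from the documents**

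- Minimum cohort size: 6 in each of four single-dose cohorts and 10 in each of three multiple-dose cohorts. Check against the stated total: 4 × 6 + 3 × 10 = 54, which agrees.
- Multiple-dose laboratory schedule (Protocol Appendix 1, footnote e): Screening, Day 1, one draw in Days 2 to 4, one in Days 5 to 14, and Posttreatment. That is three mandatory draws after Day 1. Protocol 7.5.3 also asks for tests within 24 hours of the last dose, and routine-care results are collected, so there may be more.
- Single-dose schedule (Protocol 7.5.3): Screening and within 24 hours of the infusion, so one mandatory postdose draw.

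**Categories in Table 11-2**

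Hemoglobin 1, platelets 2, white cells 2, ALT 4, AST 4, AST or ALT 4, total bilirubin 2, urea nitrogen 1, creatinine 1, ALP 1, transaminase plus bilirubin 1. Total: 23 categories in 11 parameter rows.

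Those defined by change from baseline: hemoglobin 1, platelets 2, white cells 2, bilirubin 1, urea nitrogen 1, creatinine 1, ALP 1. Total: 9.

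**What the visit counts determine**

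Let c1, c2, ... be the numbers of children positive at successive visits in a cohort of N, all observed at every visit. The number ever positive lies between max(c) and min(N, sum of c). The documents give no expected counts, so those below are assumed, with N = 10.

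| Counts by visit | Children ever positive | Percentage |
|---|---|---|
| 0, 1, 0 | exactly 1 | 10% |
| 1, 1, 0 | 1 to 2 | 10% to 20% |
| 1, 1, 1 | 1 to 3 | 10% to 30% |
| 2, 2, 2 | 2 to 6 | 20% to 60% |
| 1, 1, 1, 1 (four visits) | 1 to 4 | 10% to 40% |

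The planned table settles the number when at most one visit is positive, and gives only a range otherwise. More visits widen the range.

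**The closest-record rule**

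Suppose a child has two records under the same eCRF visit and only the one farther from the target day is an outlier. SAP 6.5 takes the other record into the summary table. If nobody else is positive, that visit shows 0 of 10, although 1 of 10 met the category. A result entered as an unscheduled visit is not affected, because SAP 11.3 includes those visits.

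**How far adverse event reporting fills the gap**

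Under Protocol 7.5.4.6, a result meeting the Appendix 2 liver criteria must be treated as clinically significant and so recorded as an adverse event. By threshold alone this covers:

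- AST or ALT above 5 × ULN: the >5, >10 and >20 categories in each of three rows, 3 × 3 = 9;
- AST or ALT above 3 × ULN with bilirubin above 2 × ULN: 1.

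That is 10 of 23 categories. The other 13 are the three >3 × ULN categories and the ten in the hemoglobin, platelet, white cell, bilirubin, urea nitrogen, creatinine and ALP rows. They become adverse events only with compatible symptoms (Appendix 2 criterion c, for transaminases), through a consequence of the result, or by investigator judgement.

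**The case against.** The best reply is that this is a display preference in a descriptive study. No figure is wrong, and the outlier table already goes beyond Protocol 9.11.3. Every result is listed by subject, and with cohorts of about 10 a count can be made from listings. All of that is true. It limits the point to a reporting improvement, but the per-child count is still unspecified.

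A second reply is that adverse events cover what matters clinically: "Any test results which are considered to be clinically significant by the investigator or subinvestigator are to be recorded as AEs". Protocol 7.5.4.6 makes a result clinically significant if it leads to treatment, further diagnostic testing, a dose change, discontinuation or a serious outcome. A reader might infer that threshold crossings would otherwise go unreported, and the documents do not support that. What remains uncovered is mainly crossings that met no mandatory trigger and were judged not significant. Adverse event terms also need not match Table 11-2: where organ toxicity is present, the toxicity is reported rather than the laboratory value.

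Two other strong readings are tempting. One is that the listings will not show Table 11-2 outliers. SAP 11.3 says "Laboratory test results will be assigned a Low/Normal/High (LNH) classification" against the normal range, and it is natural to assume that this is the listing flag. The SAP does not say so, and the available part of the listing index ends at Listing 16.2.3.1, so a flag or separate listing of outliers can be neither shown nor excluded. The other is that SAP 6.5 routinely hides abnormal values. It can do so only when two records share one eCRF visit and the worse one is farther from target, and the documents do not show how often that would occur.

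Table shells are not in the documents either, so an extra row there cannot be ruled out.

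**Conclusion.** The point holds as a low-cost reporting improvement. SAP 11.3, the table index and Protocol 9.11.3 specify no count of children who met a Table 11-2 category at least once after baseline. The gap matters mainly in the multiple-dose phase, for categories positive at two or more visits. In a cohort of 10, assumed counts of 1, 1 and 1 leave the answer anywhere from 10% to 30%. In the single-dose phase, visit and per-child counts nearly coincide, apart from unscheduled tests.

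The size rests on assumed visit counts, on three postbaseline draws and on complete data at each visit. The absence of the count rests on the visible text, without table shells or the full listing index. It does not follow that safety data are lost or that any planned figure is incorrect.

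**What to change.** In SAP 11.3 and Table 14.3.4.1.4, add a row labelled *any postbaseline value* for each Table 11-2 category, by cohort and overall within each dose phase.

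- Count each child once, over all scheduled, unscheduled and repeat postbaseline values.
- State that this row is exempt from the closest-record rule in SAP 6.5.
- Fix the denominator now. SAP 13.2.5.2 leaves room for choice ("the denominator will be selected after careful consideration of the appropriate number of subjects exposed"). Use Safety Population children with at least one postbaseline value of the parameter, and also a baseline value for the 9 change-from-baseline categories.
- Keep the planned by-visit rows unchanged.

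The cost is 23 extra rows in an existing table, a short addition to SAP 11.3, one exemption in SAP 6.5 and minor programming. No new data are needed.

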The single-dose phase will include only those subjects with normal renal function (estimated glomerular filtration rate [eGFR] ≥ 90 mL/min/1.73 m²) or mild renal impairment (eGFR 60 to < 90 mL/min/1.73 m²). See [Section 7.5.3.1.2](#) for eGFR calculations and ranges.

Table 5-2 Dosing Limits for Cefiderocol in Multiple-dose Phase: Subjects with Normal Renal Function or Mild Renal Impairment

Cohort	Multiple-dose Phase Dose		Frequency	Infusion Time
	Body Weight			
	≥ 34 kg	< 34 kg		
1 (12 to < 18 years of age)	Cohort 1 not applicable in multiple-dose phase			
2 (6 to < 12 years of age)	2000 mg	60 mg/kg*	q8h	3 hours
3 (2 to < 6 years of age)	2000 mg	60 mg/kg*	q8h	3 hours
4 (3 months to < 2 years of age)	2000 mg	60 mg/kg*	q8h	3 hours

q8h = every 8 hours

* **No more than 2000 mg of cefiderocol should be administered.**

Shorter infusion times may be allowed in the multiple-dose phase if agreed by the sponsor via the Request for Shortened Infusion Duration Form and if in the best interest of the subject. Infusion volume adjustments by age and weight will be provided in the pharmacy manual.

See [Section 7.5.3.1.2](#) for estimated glomerular filtration rate calculations and ranges.

Table 5-3 Dosing Limits for Cefiderocol in Multiple-dose Phase: Subjects with Moderate or Severe Renal Impairment

Renal Function	Multiple-dose Phase Dose					
	Body Weight \geq 34 kg			Body Weight < 34 kg		
	Dose (mg)	Frequency	Infusion Time	Dose (mg/kg)	Frequency	Infusion Time
Moderate renal impairment (eGFR 30 to < 60 mL/min/1.73 m ²)	1500	q8h	3 hours	45	q8h	3 hours
Severe renal impairment (eGFR 15 to < 30 mL/min/1.73 m ²)	1000	q8h	3 hours	30	q8h	3 hours

eGFR = estimated glomerular filtration rate; q8h = every 8 hours

Shorter infusion times may be allowed in the multiple-dose phase if agreed by the sponsor via the Request for Shortened Infusion Duration Form and if in the best interest of the subject. Infusion volume adjustments by age and weight will be provided in the pharmacy manual.

Expected total duration of cefiderocol administration is 5 to 14 days. A minimum of 6 doses will be permissible if, in the opinion of the investigator, it is in the subject's best interest.

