7.5.3.1.2 Estimated Glomerular Filtration Rate

Estimated GFR will be measured at Screening for subjects in the single-dose phase. In the multiple-dose phase, eGFR should be estimated at Screening and daily during treatment, if clinically indicated. Dose adjustments should be made reflecting the current CrCL ([Section 5.2](#)).

For ages ≥ 3 months to < 1 year, the eGFR will be based on the Schwartz equation [[10](#)]:

$$\text{eGFR} = 0.45 \times (\text{height/Scr}), \text{ if height is expressed in centimeters}$$

For ages ≥ 1 year to < 18 years, the eGFR will be based on the modified Bedside Schwartz equation [[11](#)]:

$$\text{eGFR} = 0.413 \times (\text{height/Scr}), \text{ if height is expressed in centimeters}$$

OR

$$41.3 \times (\text{height/Scr}), \text{ if height is expressed in meters}$$

eGFR (estimated glomerular filtration rate) = mL/min/1.73 m²

Scr (standardized serum creatinine) = mg/dL

Renal function ranges are provided in [Table 7-6](#).

Table 7-6 Renal Function Ranges

Renal Impairment	Estimated Glomerular Filtration Rate (eGFR)
None (normal)	≥ 90 mL/min/1.73 m ²
Mild	60 to < 90 mL/min/1.73 m ²
Moderate	30 to < 60 mL/min/1.73 m ²
Severe	15 to < 30 mL/min/1.73 m ²

The single-dose phase will enroll subjects with an eGFR of ≥ 60 mL/min/1.73 m².

The multiple-dose phase will enroll subjects with an eGFR of ≥ 15 mL/min/1.73 m².

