4.1. Safety Endpoints

The following safety and tolerability endpoints will be evaluated:

- Adverse Events
 - Treatment-emergent adverse events (TEAEs), treatment-emergent serious adverse events (SAEs), treatment-related TEAEs and TEAEs leading to discontinuation of study drug
 - Special Situations – Abuse, Misuse, Overdose and Medication Error
- Vital signs (blood pressure, pulse rate, respiratory rate, body temperature)
 - observed and change from baseline values
- Clinical laboratory assessments
 - Routine lab tests (hematology, blood chemistry, urinalysis)
 - observed and change from baseline values
 - Estimated glomerular filtration rate (eGFR)
 - Urine pregnancy test
 - Microbiologic cultures
- Physical examination findings

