11.3. Laboratory Evaluations

Clinical laboratory tests will be performed at prespecified time points per the Time and Events Schedule in Appendix 1 of the protocol.

Routine hematology, blood chemistry, and urinalysis parameters that will be assessed are presented in Table 11-1.

This document is confidential.

Table 11-1 Routine Laboratory Tests

Category	Evaluation Parameters	
Hematology tests	Hematocrit Hemoglobin Platelet count	White blood cell count Differential white blood cell count
Blood chemistry tests	Aspartate aminotransferase Alanine aminotransferase Gamma glutamyltransferase Alkaline phosphatase Direct* and total bilirubin Indirect bilirubin* Total protein Albumin	C-reactive protein Blood urea nitrogen Serum creatinine Blood glucose Uric acid Electrolytes (sodium, potassium, chloride, calcium, magnesium, and bicarbonate)
Urinalysis	Microscopic analysis Protein Glucose Bilirubin	Urobilinogen Occult blood Leukocyte esterase

* If clinically indicated

Estimated GFR (eGFR) will be measured as noted below at Screening and predose if more than 24 hours after Screening) for subjects in the single-dose phase. In the multiple-dose phase, eGFR will be estimated at Screening and daily during treatment, if clinically indicated. Dose adjustments will be made following the recommendations in Table 3-4.

Estimated GFR

For ages ≥ 3 months to < 1 year, the eGFR will be based on the Schwartz equation (1984)²:

$$\text{eGFR} = 0.45 \times (\text{height}/\text{Scr}), \text{ if height is expressed in centimeters}$$

For ages ≥ 1 year to < 18 years, the eGFR will be based on the modified Bedside

Schwartz equation (2009)

$$\text{eGFR} = 0.413 \times (\text{height}/\text{Scr}), \text{ if height is expressed in centimeters}$$

OR

$$41.3 \times (\text{height}/\text{Scr}), \text{ if height is expressed in meters}$$

$$\text{eGFR (estimated glomerular filtration rate)} = \text{mL/min}/1.73 \text{ m}^2$$

This document is confidential.

Scr (standardized serum creatinine) = mg/dL

A list of the reference ranges for all clinical laboratory tests conducted will be provided by the study site prior to initiation of the study and updated by the study site if changes to the reference ranges are implemented during the study conduct.

The investigator or subinvestigator will assess whether any abnormal changes from Screening (within 48 hours prior to the administration of the first dose of cefiderocol) are clinically significant.

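### SAP Table 11-2 counts creatinine only at an absolute rise of 0.3 mg/dL or more, so a halving of eGFR goes uncounted when baseline creatinine is below 0.3 mg/dL, mainly in Cohort 4

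*SAP*

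**What the plan says.** SAP 11.3 plans a count and percentage of subjects in each Table 11-2 outlier category at each postbaseline visit, by cohort. The only serum creatinine entry is "Increase from baseline ≥ 0.3 mg/dL". It has no percentage or fold-change counterpart. In the same table, blood urea nitrogen, total bilirubin and ALP each have a rise of at least 50% combined with a value above the upper limit of normal.

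SAP 4.1 names eGFR among the safety endpoints. For analysis, SAP 11.3 says: "The eGFR and microbiology data (urine and blood collection of microbiological cultures) will be listed". SAP 7.2 summarises eGFR as a baseline characteristic, but the index of tables contains no post-baseline eGFR table.

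The eGFR equations are in SAP 11.3 and Protocol 7.5.3.1.2. "For ages ≥ 3 months to < 1 year, the eGFR will be based on the Schwartz equation", with constant 0.45. "For ages ≥ 1 year to < 18 years, the eGFR will be based on the modified Bedside" Schwartz equation, with constant 0.413. Height is in centimetres and "Scr (standardized serum creatinine) = mg/dL". Protocol 5.2 defines "normal renal function (estimated glomerular filtration rate [eGFR] ≥ 90 mL/min/1.73 m²", with no upper limit. Protocol Table 7-6 puts moderate impairment at 30 to under 60.

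**The concern.** In these equations creatinine at a given eGFR is proportional to height. A fixed 0.3 mg/dL is therefore a modest relative change in a tall adolescent and can be more than a doubling in an infant. A single absolute cut-off applies a much less sensitive rule to the smallest children.

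This matters because safety is a primary objective, more than 90% of a dose is excreted unchanged in urine (Protocol 1.2), and Protocol 3.2 describes Cohort 4 as not having reached renal maturation, with less predictable clearance. The table that counts renal outliers is least sensitive in that cohort.

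**Working it through.** The SAP gives no derivation for the 0.3 mg/dL cut-off, so there is no planned figure to reproduce. The check inverts the plan's equations.

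**Inputs.** From the documents: k = 0.45 under 1 year, k = 0.413 from 1 year, the 0.3 mg/dL cut-off, and the renal function classes. The documents give no heights. Assumed lengths are about 60 cm at 3 months, 67 cm at 6 months, 75 cm at 1 year, 87 cm at 2 years and 115 cm at 6 years, with 100 cm as a point within Cohort 3.

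**Formula.** Scr = k × height / eGFR. With height and k fixed, halving eGFR doubles Scr, so the rise equals the baseline value. A halving is therefore counted only if baseline Scr is at least 0.3 mg/dL, that is, if baseline eGFR is at most k × height / 0.3.

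| Length, k | Baseline Scr at eGFR 90 | Baseline Scr at eGFR 120 | Baseline eGFR above which a halving is uncounted |
|---|---|---|---|
| 60 cm, 0.45 | 0.300 | 0.225 | 90 |
| 67 cm, 0.45 | 0.335 | 0.251 | 100.5 |
| 75 cm, 0.45 | 0.375 | 0.281 | 112.5 |
| 75 cm, 0.413 | 0.344 | 0.258 | 103 |
| 87 cm, 0.413 | 0.399 | 0.299 | 120 |
| 100 cm, 0.413 | 0.459 | 0.344 | 138 |
| 115 cm, 0.413 | 0.528 | 0.396 | 158 |

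The first five rows span Cohort 4, and 87 to 115 cm spans Cohort 3.

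**Worked case.** Take a 60 cm infant with eGFR 120.
- Baseline Scr = 0.45 × 60 / 120 = 0.225 mg/dL.
- A rise of 0.29 is 0.29 / 0.225 = 129% and is not counted.
- eGFR is then 27 / 0.515 = 52, in the moderate class.
- The flag needs Scr of 0.525, a 2.33-fold rise, at which eGFR is 27 / 0.525 = 51, a fall of 57%.

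**Where absolute and relative rules agree.** A rise of 0.3 is a 50% rise when baseline is 0.6 mg/dL. At eGFR 90 that needs a height of 90 × 0.6 / 0.413 = 131 cm. Below a baseline of 0.6 mg/dL, the absolute rule is less sensitive than a 50% rule.

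**Effect of a 50% row.** Creatinine at 1.5 times baseline means eGFR at 1 / 1.5 of baseline, a one-third fall at any height. For the 60 cm infant this is Scr 0.3375 and eGFR 27 / 0.3375 = 80.

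**The case against.** The strongest reply is that the miss is conditional and other outputs cover much of it.

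**The condition.** This stands. A reader might infer that the rule misses every halving in infants and toddlers because their normal creatinine is 0.2 to 0.3 mg/dL. The documents do not support that. The range needs assumed lengths and an eGFR near 120 or more; over eGFR 90 to 150 at the Cohort 4 lengths it is about 0.18 to 0.40. From eGFR 90, the plan's lower limit of normal, a halving is counted at every Cohort 4 length in the table, though exactly at the cut-off at 60 cm. Low-normal children can still change class uncounted: from eGFR 90, a rise of 0.29 gives 27 / 0.590 = 46 at 60 cm and 35.93 / 0.689 = 52 at 87 cm. Neither is a halving.

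**Cohort 3.** A reader might extend the halving argument fully to this cohort. At 100 cm and eGFR 120, a halving raises creatinine by 0.344 and is counted. An uncounted rise of 0.29 leaves eGFR at 65, still mild.

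**Other outputs.** A reader might infer that no summary would show the event. That is wrong. Creatinine has change-from-baseline summaries, blood urea nitrogen has its own outlier row, and High/Low flags and eGFR appear in listings. Protocol 7.5.4.6 treats a laboratory result that changes dosing as clinically significant and hence an adverse event. Because Protocol Table 5-3 has a separate dosing row for moderate impairment, the worked case would reach the adverse event tables if dosing were changed.

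These routes do not replace the count. In a cohort of 10, one rise of 0.29 moves the mean by 0.029 mg/dL. The blood urea nitrogen row also requires a value above the upper limit of normal. The dosing-change route does not operate in the single-dose phase. With minimum Cohort 4 sizes of 6 and 10, a careful reader of the listings could still find such cases, which limits the harm.

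**Conclusion.** The concern holds for the tabulated outlier count. That a halving is uncounted whenever baseline creatinine is below 0.3 mg/dL follows from the plan's equations and needs no outside figure. Placing this mainly in Cohort 4, at baseline eGFR above about 90 to 120, rests on assumed lengths of 60 to 87 cm. How many enrolled children would be affected cannot be derived, because the documents give no baseline eGFR distribution.

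The consequence is an understated count of renal outliers, mainly in the youngest cohort. A claim that the plan is blind to renal harm there would go too far. This is a worthwhile, inexpensive improvement to reporting.

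**What to change.** Keep the 0.3 mg/dL row in SAP Table 11-2 and add one: serum creatinine increase from baseline of at least 50%. Present both by cohort and phase. The new row fits the percentage criteria already used for other parameters in that table.

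Optionally, add a shift table of baseline versus worst post-baseline eGFR class. Protocol 7.5.3.1.2 schedules eGFR only at Screening in the single-dose phase, and during multiple dosing only if clinically indicated. The SAP should therefore state that post-baseline eGFR is derived from each creatinine value and the recorded height. Use the Table 7-6 classes plus a class below 15, since Table 7-6 stops there.

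The cost is one table row and, if wanted, one shift table, with no new data collection. The downside is false flags at very low creatinine: a reporting step from 0.2 to 0.3 mg/dL is already a 50% rise. Showing both rows lets the reader see which flags rest on the relative rule alone. The change affects reporting only and proposes no dose or clinical rule.
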